- After Session 5: \$20 for phone session, up to \$15 for daily monitoring
- After Session 6: \$20 for phone session, up to \$15 for daily monitoring
- After Session 7: \$20 for phone session, up to \$15 for daily monitoring
- After Session 8: \$20 for phone session, plus up to \$15 for daily monitoring

- After Week 16 visit to the VA: \$40 for questionnaire, plus up to \$15 for daily monitoring
- After Week 20 Booster Session: \$20
- After Week 24 questionnaire: \$40

Study Schedule

Participants in the waitlist-controlled trial will be enrolled in the study for a total of 24 weeks (168 days), whether they are in the intervention or waitlist-control group. They will participate in eight intervention sessions and one booster session. The first and last sessions will take 1.5-2 hours, depending on how long the participants take to complete the surveys. Sessions 2-8 and the booster session will take 30 minutes each. After each intervention session, they will complete a short 5-minute questionnaire on their mobile phones. During the intervention, they will also complete two daily assessments, which will take approximately 20 minutes total. Each participant will also complete two additional assessment batteries, which will take 45-60 minutes. Thus, the total time commitment is approximately 27-28 hours. On the rare occasion when study visits may be unexpectedly delayed, visits will not be delayed more than 1 week. See the following flowchart for detailed information about the participant timeline.

Patient Compensation

Participants will receive the following:

- \$20 for attending all intervention sessions via videoconferencing or phone (including booster session – 9 sessions)
- \$1 for each completed breathalyzer reading (up to 14/week, with \$1 bonus for completing all readings)
- \$30, \$40, \$40, and \$40 for completing health questionnaires
- TOTAL POSSIBLE: \$450

5. Data

Collection and record keeping

Both intervention and waitlist-control groups will complete an extensive assessment battery at baseline, 8 weeks, 16 weeks, and 24 weeks. They will also complete daily monitoring of alcohol and medication use during their 8-week intervention period. The following outcome variables will be explored via the listed methods of data collection:

Confidential online questionnaires, completed on tablets or mobile phones at baseline, and 8-, 16-, and 24 week follow-ups, concerning the following variables:

- Post-Traumatic Stress Disorder Symptoms

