In the event that identifying information is released to an unauthorized party, the serostatus of participants could be revealed to unwanted individuals. This could potentially cause harm, but is unlikely considering the careful plans in place regarding data management and protection. All possible measures will be taken to protect information provided through surveys, interviews, and intervention participation, and confidentiality will be respected. Following completion of data collection, responses will become anonymous as identifying information is permanently deleted. For these reasons, we estimate that this minimally-invasive project poses minimal risk.

STATISTICAL ANALYSIS PLAN

For the randomized controlled trial, data analytic methods will be focused on examining acceptability and feasibility, as well as effects on alcohol intake, HAART adherence, and HIV-related medical outcomes (CD4 count and viral load). Intervention adherence, daily monitoring adherence, and session acceptability will be described using descriptive statistics. Session attitudes will be assessed using several 5-point semantic differential attitudinal measures rating the session, including Boring/Interesting, Unpleasant/Pleasant, Bad/Good, Useless/Useful, and Negative/Positive. Scores on the session attitude semantic differential measures will be reverse-coded where required and averaged to form an overall attitude score, with “0” being “neutral.”

We will provide descriptive summaries for the outcome variables, including mean, median, and standard deviation for continuous variables and counts and percentages for categorical variables. We will summarize the outcome variables overall and across the intervention groups. In assessing the differences in alcohol use and medication adherence between the two groups during the 8-week intervention period, we will utilize the Kruskal–Walli’s test, a non-parametric statistical approach, to compare the distribution of outcome variables. The general linear model (ANOVA) will be used to estimate the difference between alcohol use and medication adherence among the groups, and the estimation of the effect size (Cohen’s D) at the end of the 8-week intervention period. While this study was not powered to detect significant differences, the goal of these analyses is to observe changes and effect sizes that may provide preliminary evidence of efficacy.

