To examine intervention effects as assessed through daily surveys, we will examine responses to the morning survey question asking if participants had consumed alcohol on the previous day (yes/no), whether or not they reported a positive breathalyzer reading (> 0.0), and if they had taken all of their HAART on the previous day (yes/no). Within the 8-week intervention period and using the daily data, we will assess the change in the proportion of participant's alcohol use, the proportion of positive breathalyzer readings, and the proportion of their medication use from the beginning of week 1 to the end of week 8 using McNemar's matched pair test. This test will allow us to address the interdependency in the repeated measurements. We will account for missing survey responses by considering two scenarios: First, assuming they were missing completely at random and remained missing, and second, that missing values were indicative of alcohol use/medication nonadherence and were thus filled in as drinking days/positive breathalyzers/nonadherent days (a conservative approach).

All participants will have received the intervention by the end of the 8 week (2-month) post-intervention period. To examine long-term intervention effects, participants from both the waitlist-control and intervention group will be combined into a single dataset. A generalized linear model (via SAS GENMOD PROCEDURE) and a multiple linear regression model will be fit to the change from baseline for each outcome measure. Change from baseline is the difference between the baseline value and values obtained at subsequent time points: 8 weeks (immediate post-intervention; T2 for intervention group and T3 for waitlist-control), and 16 weeks (2 months post-intervention; T3 for intervention group and T4 for waitlist-control) for each outcome measure. The rationale for fitting the change from baseline is that this model removes the effect of baseline differences that may exist from the model. All statistical hypothesis tests will be conducted using the standard 5% significance level. SAS Version 9.4 (TS1M1, SAS Institute, Cary, NC), will be used for all analyses.

References

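### Medication adherence is compared between arms at week 8 and modelled as change from baseline, but no listed data source supplies the waitlist, baseline or 2-month values

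*Combined protocol and SAP*

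**What the plan says.** The second paragraph of the Statistical Analysis Plan sets up the randomised comparison: "In assessing the differences in alcohol use and medication adherence between the two groups during the 8-week intervention period", a Kruskal-Wallis test is used. It then adds an estimate and Cohen's d at the end of the 8 weeks: "The general linear model (ANOVA) will be used to estimate the difference between alcohol use and medication adherence among the groups".

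The fourth paragraph pools both arms and specifies models that "will be fit to the change from baseline for each outcome measure". The first follow-up time is "8 weeks (immediate post-intervention; T2 for intervention group and T3 for waitlist-control". The later one is given as "16 weeks (2 months post-intervention; T3 for intervention group and T4 for waitlist-control".

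The third paragraph is a separate within-person analysis of the daily surveys. It uses McNemar's test and includes "the proportion of their medication use from the beginning of week 1 to the end of week 8".

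Protocol section 5 (Data, Collection and record keeping) says where the data come from: "The following outcome variables will be explored via the listed methods of data collection". On the daily surveys it says: "They will also complete daily monitoring of alcohol and medication use during their 8-week intervention period". Medication use appears in the list once, under the twice-daily phone surveys. The topics for the baseline, 8-, 16- and 24-week questionnaires include alcohol and drug use, but nothing on HIV medication or adherence.

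**The concern.** The waitlist arm does not begin TRAC, and so does not begin daily monitoring, until the randomised 8 weeks are over. If daily monitoring is the only source of adherence data, the between-arm adherence comparison has data in one arm only. The change-from-baseline models have no baseline and no 2-month value in either arm.

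Adherence is one of the five research questions, and one of the two outcomes in the only analysis that uses the randomisation. The SAP gives changes and effect sizes as the purpose of these analyses, since the trial is not powered. A missing adherence effect size is therefore a missing deliverable. What remains is the McNemar analysis, which has no control group. A self-report that was never asked at week 8 cannot be recovered afterwards.

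**Working it through.** The documents give no figure to reproduce on this point, so the check sets the values the SAP needs against the sources the protocol lists.

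**Candidate sources**

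- *Twice-daily surveys.* In the intervention arm they run from the day after Session 1 to the end of week 8 (Step 3a, item 6). In the waitlist arm Session 1 is at week 8 and monitoring starts the day after (Step 3b, items 6 and 10).
- *Questionnaires at baseline, 8, 16 and 24 weeks.* No adherence topic is listed (section 5).
- *Screener.* It has one question on the share of doses taken over the past month (Step 1, item 6b), but item 10 of the same step rules out screening data for study use.
- *Prescription data from VA databases.* Their stated use is to build the list of patients to screen (section 4, Study Population and patient selection). No refill-based measure is defined.
- *Chart review.* Viral load only (Steps 3a and 3b; section 5).
- *Waitlist contact at week 4.* Retention and adverse events only (Step 3b, item 3).

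**Values needed against listed source**

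| Arm and time | Needed for | Listed source |
|---|---|---|
| Intervention T1 (baseline) | change models | none |
| Intervention T2 (week 8) | week-8 comparison, change models | daily surveys |
| Intervention T3 (week 16) | change models | none |
| Waitlist T1 (enrolment) | change models, if this is the baseline | none |
| Waitlist T2 (week 8) | week-8 comparison; also baseline on the other reading | none |
| Waitlist T3 (week 16) | change models | daily surveys |
| Waitlist T4 (week 24) | change models | none |

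The SAP does not say whether the waitlist baseline is T1 or T2. Its 8-week and 16-week labels for waitlist T3 and T4 also fit a count from T2.

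- Baseline = T1: 3 + 4 = 7 values needed, 2 sourced.
- Baseline = T2: 3 + 3 = 6 values needed, 2 sourced.
- Week-8 comparison: 1 of 2 arms sourced.
- Change scores: 2 arms × 2 times = 4. Each needs a baseline value that has no source, so 0 of 4 on either reading.
- Sensitivity: if week-1 daily responses stood in for baseline, intervention T2 and waitlist T3 changes could be formed (2 of 4). The 2-month changes still could not (0 of 2).

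**Check that the waitlist arm is not monitored in weeks 0-8**

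- *Payments.* Nine sessions at $20, eight weeks of monitoring at $15 (14 readings plus a $1 bonus), and questionnaires at $30 + 3 × $40 = $150 give 180 + 120 + 150 = $450. This is the stated total. Sixteen weeks of monitoring would give 180 + 240 + 150 = $570. The waitlist payment schedule has no monitoring payment before Session 2.
- *Time.* At 20 minutes a day, 16 weeks of daily surveys would take 112 × 20 / 60 = 37.3 hours. That alone exceeds the stated total commitment of 27-28 hours.

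**The case against.** The strongest reply is that section 5 is a list of topics and the questionnaires themselves are not in the documents. An adherence scale may be in the battery and simply missing from the list. Two features make this plausible. The SAP introduces its daily-survey analysis as a separate block, which suggests that the between-arm analysis was meant to rest on the questionnaires. The reference list also includes a study of one-month self-reported adherence. This stands as a limit on the conclusion, which concerns what is specified and not what was collected. It does not remove the problem: section 5 presents the list as the outcome variables with their methods, and the SAP names no adherence instrument, scale or time point. Even if an item exists, the measure could be chosen after the data are seen.

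A second reply is that the first morning survey asks about the previous day, which gives one day close to baseline. That is not the baseline assessment, and in the waitlist arm it falls at week 8.

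The count of 2 sourced values can also be questioned. It treats daily yes/no reports as a T2 or T3 value without an aggregation rule. It also credits waitlist T3, although Step 3b item 10d ends monitoring on the day of the final intervention session, which may be Session 8, a week before the post-intervention visit. Both points would lower the count, so it errs in the plan's favour.

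Finally, this is an unpowered pilot of 50 with feasibility aims and no designated primary outcome. That limits the severity, and the alcohol comparison and the McNemar analysis are untouched.

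**Conclusion.** The concern holds. As documented, the randomised adherence comparison has a source in one of two arms, 2 of 7 (or 2 of 6) required values are covered, and none of the 4 change scores can be formed. All of these counts assume that the questionnaires contain no unlisted adherence item; one such item, asked at all four times in both arms, would fill every gap. The point should be fixed, but it does not undermine the trial as a whole, because alcohol use is in the questionnaire list for both arms at all four times.

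**What to change.** 1. Check the questionnaires. If they already contain an adherence item, add it to the list in section 5 and name it in the SAP.
2. If they do not, and the time points are still open, put the screener's existing past-month question into the baseline, 8-, 16- and 24-week questionnaires in both arms. The waitlist week-8 questionnaire should be completed before Session 1, as Step 3b already orders it (item 7 before item 9).
3. In the SAP, name that item as the adherence outcome for the week-8 comparison and the change-from-baseline models. State whether the waitlist baseline is T1 or T2, and that the daily HAART question feeds only the within-person McNemar analysis.
4. If the window has passed and no item exists, restrict the adherence conclusions to the uncontrolled within-person analysis and say so. Prescription records might support a refill-based measure, but it would have to be defined first.

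The cost is one question, already written, in four existing electronic questionnaires, and a few sentences in the SAP. The drawback is a single self-report item. Its one-month recall means that the week-8 answer covers only about the second half of the randomised period.

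A minor separate point: CD4 count is a named outcome, but the chart review steps extract only viral load. Add CD4 to the extraction or remove it as an outcome.

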Patients who are identified as eligible will be screened using a survey if they are interested in participating. First, they will be asked if they sometimes drink alcoholic beverages. If yes, they will be asked how many times in the past month they have had 5 or more drinks in a day (for men) or 4 or more drinks in a day (for women). They will also be asked if, on any week in the past month, they have had more than 14 drinks (for men) or more than 7 drinks (for women). If they answer yes to either of those questions, they are considered to be an at-risk drinker and will qualify for the study. This screening may also be conducted over the phone if the participant indicates interest in the study but is unable to complete the screening procedure while visiting the clinic. If the screening procedure indicates that the participant is eligible, they may begin the study within 30 days time.

Subject Exclusion Criteria: Individuals who are HIV-negative, less than 18 years of age, who are not identified as an at-risk drinker through the alcohol screener, or who are not currently prescribed HIV medication will not be eligible to participate. For the randomized controlled trial, participants who have not had their viral load tested within the 3 months prior to beginning the intervention (3 months before baseline for the Intervention group, 3 months before the 8-week time point for the Waitlist-Control group) will not be eligible to begin the study until they have had bloodwork completed. Additionally, participants will take the AUDIT questionnaire as part of the study screener. If they score a 20 or higher, indicating alcohol dependence, they will not be eligible for study participation.

Study Recruitment

After screening, patients who are deemed eligible for the study may be recruited in the following ways:

- An IRB approved letter mailed to the patient and then after two weeks the patient may be contacted over the phone or in person at a clinic visit about the study unless they decline
- Through an approved study flyer or direct patient initiated contact to the study coordinator
- A clinic provider refers patient to study or gives patient study flyer at clinic visit

- Direct patient contact in the clinic at clinic visit
- Outreach to a patient who has previously signed an informed consent form for another research study which allowed for future contact

Study Intervention/Investigational Product

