 - i. The research coordinator will check the participant's medical record to make sure they have had their viral load tested within the previous 3 months. If not, their entry in the study will be delayed until after they have obtained viral load testing.
 - ii. The research coordinator will inform the participant that they have been placed in the Intervention group.
 - iii. The coordinator will schedule the participant's first videoconferencing session (1 ½-2 hours) with the study interventionist using the shared calendar, where they will receive their smartphone (if needed) and breathalyzer
 - iv. The research coordinator will provide the participant with a copy of the Participant Manual, which includes instructions for downloading the breathalyzer app on to their own phone, if they choose to use it.
 - v. The coordinator will encourage the participant to try downloading the app, and tell them that the interventionist will be in touch soon and can help them to install the app if need be
 - b. If they are in the waitlist-control group (Group 2):
 - i. The research coordinator will check the participant's medical record to make sure they have had their viral load tested within the previous 1 month (within 3 months of the intervention starting), or has plans to get it tested within the following 2 months. If not, their entry in the study will be delayed until after they have obtained viral load testing.
 - ii. The research coordinator will inform the participant that they have been placed in the waitlist-control group
 - iii. The participant will be provided the chance to complete the baseline assessment at that time on a laptop computer. If they choose not to complete it, the interventionist will call them to provide introductions and give them the web address for completing the questionnaire. This web address will also be provided to the participant on a handout.
6. The research coordinator will ask the participant the following questions about their cell phone:
 - a. Do you prefer to use a study phone or your own phone? (Study Phone/Own Phone)
 - b. If they prefer to use their own phone:
 - i. Do you own a smartphone? (Y/N)
 1. If no, inform participant that they must use a study phone, which will be provided at their first appointment
 - ii. What type of phone is it? (Android/iPhone/Windows/Other)

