2. Upon arrival to the clinic for the first intervention session, the patients will be shown to a private room to begin their first videoconferencing session
3. The patient will be given a laptop to complete the initial assessment battery
4. If the participant is in need of a study phone, the VA coordinator will provide this phone, along with the breathalyzer, to the participant
5. Participants will begin the first intervention session, which will consist of the following content/tasks:
 - a. Introductions and orientation to the technology (smartphone and breathalyzer, stored at the clinic; tutorial handouts provided)
 - b. Review of self-monitoring procedures and setting of "do not disturb" hours
 - c. Review of breathing awareness exercise
 - d. Scheduling follow-up intervention sessions for weeks 2-8, conducted via mobile phone
 - e. A short post-session satisfaction survey, delivered via text message and completed immediately following the session.
6. The day after the first session, participants will begin self-monitoring their alcohol, medication use, and mental health
 - a. They will be texted at two random times each day using an automated software to complete a breathalyzer reading and finish a survey
 - b. If participants do not respond to the request within 30 minutes, a text reminder will be sent, followed by another an hour later.
 - i. If the participant is in a situation where they are unable to complete the breathalyzer test, they will be able to respond to the text message and request a follow-up reminder two hours later.
 - c. If participants wish to go to sleep for the night and have not yet received their evening reminder, they can elect to complete a breathalyzer reading and survey before going to bed.
 - d. Self-monitoring will continue through the end of week 8 (until they return to the VA to complete their post-test and return their equipment)
 - e. Participants will be instructed to call the interventionist if they have any technical difficulties throughout the course of the study
7. Sessions 2-8 of the intervention will be conducted via phone call, with patients instructed to find a private room at home from which to speak with their counselor.
 - a. After each session, the participant will complete a short post-session satisfaction survey, delivered via text message and completed immediately following the session

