 - i. If patients cannot be reached, researchers will attempt to contact them three additional times (one day later, three days later, and one week later). If they cannot be contacted by the third attempt, they will be considered lost to follow-up and will not be contacted again.
13. After the participant completes the study, a retrospective chart review will be conducted to obtain viral load measurements (minimum of 2) from the participant during the time period beginning 3 months prior to their entry into the study and up to 6 months after their entry into the study.

3b. Waitlist-control group

1. After randomization and enrollment, the participant will complete the baseline assessment either at the time of enrollment, at home, or during a subsequent appointment within the next 30 days
2. The interventionist will call the participant after enrollment and do the following:
 - a. Introduce themselves to the patient
 - b. Describe the study timeline
 - c. Discuss follow-up contact times and encourage the participant to stay in contact
 - d. Remind participant of incentives they will receive for participating
 - e. Provide information about the baseline assessment (if the participant has not already completed it)
3. The interventionist will contact participants using their chosen method of communication after 4 weeks to maintain contact and ensure that no adverse events have occurred
4. At 7 weeks, the interventionist will contact participants to obtain their availability for the next week to schedule the first intervention content session based on the shared calendar
5. One day before the videoconferencing session, the researcher will contact the participant via the participant's chosen method of contact to remind them of their appointment
6. At 8 weeks, the patient will come into the clinic to begin the intervention.
7. The patient will be given a laptop to complete the initial assessment battery
8. If the participant is in need of a study phone, the VA coordinator will provide this phone, along with the breathalyzer, to the participant
9. The participant will begin the first intervention session, which will consist of the following content/tasks:
 - a. Introductions and orientation to the technology (smartphone and breathalyzer, stored at the clinic; tutorial handouts provided)

- b. Review of self-monitoring procedures and setting of “do not disturb” hours
 - c. Review of breathing awareness exercise

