- Alcohol and drug use
- Alcohol-related beliefs
- Mental health status (anxiety, depression, stress, history of mental health diagnoses)
- Coping processes
- Emotion regulation
- Coping self-efficacy
- Quality of life
- Perceived social support
- Perceived HIV stigma
- HIV diagnosis date and transmission source
- Technology use
- Technology attitudes
- Health literacy
- Demographic information
- COVID-19-related history, protective behaviors, attitudes, and beliefs
- Knowledge of intervention materials (follow-up only)

Confidential online questionnaires and correspondence, completed on mobile phones twice daily, concerning the following variables:

- Alcohol intake, via survey response
- Medication use, via survey response
- Engagement in COVID-10 protective behaviors and COVID-19 related stress, via survey response
- Blood alcohol content, via breathalyzer reading sent to study coordinator
- Anxiety and depression, via survey response

Confidential online questionnaires, completed on tablets or mobile phones immediately following each of the 8 intervention sessions and concerning the following variables:

- Ratings of session experiences
- Attitudes toward session
- Perceived therapeutic alliance
- Open-ended reaction to the session

Retrospective chart review of viral load based on blood draws conducted as part of routine clinical care.

Data Storage

All survey and questionnaire data will be collected using Qualtrics survey software, which encrypts data and utilizes password-protected accounts. The "Anonymize Responses" option will be selected to avoid collection of IP addresses. Participants will only be asked to include their numeric study ID as part of their survey response, and will not need to provide any other identifying information. Any downloaded data will be kept on password-protected computers. Once data collection is completed and data files have been downloaded to a local computer, the data on Qualtrics will be deleted. The Qualtrics surveys will be housed

on the University of Georgia's Qualtrics account, which is used by the study interventionist and coordinator. The funder PI, [name], is at the University of Kentucky and will have shared access to the de-identified datasets.

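### The week-8 comparison of alcohol use between arms leaves out the baseline value that both arms supply and reports Cohen's d without a confidence interval; adding both is a cheap improvement

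*Combined protocol and SAP*

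**What the plan says.** The second paragraph of the Statistical Analysis Plan covers the two-arm comparison over the first eight weeks. It plans a Kruskal-Wallis test and then a model: "The general linear model (ANOVA) will be used to estimate the difference between alcohol use and medication adherence among the groups". The same sentence places the estimate and Cohen's d at the close of the eight-week intervention period. No covariate is named, and no confidence interval is mentioned there or elsewhere in the documents. The paragraph says the study was not powered for significance and that its aim is effect sizes as preliminary evidence of efficacy.

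The data for an adjustment are planned. Under section 5 (Collection and record keeping), both groups "complete an extensive assessment battery at baseline, 8 weeks, 16 weeks, and 24 weeks", and the list of questionnaire variables includes "Alcohol and drug use".

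Baseline is completed after the arm is known. In Step 2 (Patient Enrollment), item 5a: "The research coordinator will inform the participant that they have been placed in the Intervention group". Those participants answer the battery later, at the first session visit (3a, item 3): "The patient will be given a laptop to complete the initial assessment battery". In the waitlist arm, disclosure is followed by an offer (item 5b): "The participant will be provided the chance to complete the baseline assessment at that time on a laptop computer". Section 3b, item 1 lets it be done "either at the time of enrollment, at home, or during a subsequent appointment within the next 30 days".

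**The concern.** At week 8 one randomised arm has had the intervention and the other has not. The other effect analyses in the SAP do not make that comparison. The daily-data analysis is within participant. The long-term model uses change from baseline, but pools both arms and counts eight weeks from the start of each arm's own intervention. The SAP justifies that model by the removal of baseline differences, yet does not carry the idea to the randomised comparison.

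The stated product of the week-8 analysis is an effect size. With about 50 participants, a d printed alone tells a reader little: assuming 25 per arm, an observed d of 0.5 has a 95% CI from -0.07 to 1.06. If baseline drinking predicts week-8 drinking, part of that width can be removed with data already planned.

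**Working it through.** **Inputs.** The target of 50 is from section 3 (Study Objectives). The documents give no allocation ratio, SD, dropout rate or correlation, and no power or precision figure to reproduce. Assumed: 25 per arm, normal theory, equal SDs at both times, no missing data, and a correlation rho between baseline and week-8 alcohol use of 0.3, 0.5 or 0.7. Eligibility could push rho down, because entry requires at-risk drinking while the upper end is cut off: "If they score a 20 or higher, indicating alcohol dependence, they will not be eligible for study participation". All widths are in SD units.

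**Unadjusted half-width** = t(0.975, N-2) × sqrt(1/n1 + 1/n2) = 2.011 × sqrt(0.08) = 0.569.

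**ANCOVA half-width** = t(0.975, N-3) × sqrt[(1 - rho²)(1/n1 + 1/n2)(1 + 1/(N-4))]. At rho 0.5: 2.012 × sqrt(0.75 × 0.08 × 47/46) = 0.498.

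| rho | 25 per arm | Narrower by | Equivalent unadjusted N | 20 per arm |
|---|---|---|---|---|
| unadjusted | 0.569 | – | 50 | 0.640 |
| 0.3 | 0.549 | 3.5% | 53.8 | 0.620 |
| 0.5 | 0.498 | 12% | 65.2 | 0.563 |
| 0.7 | 0.411 | 28% | 96.0 | 0.464 |

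Equivalent N is 50 / [(1 - rho²) × 47/46]. Break-even is at rho of about 0.15 (0.17 with 20 per arm). At rho 0 the cost is about 1% (0.575 against 0.569).

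**Disclosure before baseline.** If knowing the arm shifts one arm's reported baseline by delta SD, the adjusted estimate is biased by rho × delta. At delta 0.2 that is 0.06, 0.10 or 0.14 SD. In a simulation of 40,000 trials with no effect, CI coverage was then 94.6%, 93.1% or 89.9%. Total error (RMSE) stays below that of the unadjusted estimate until delta reaches sqrt(V_unadjusted - V_ANCOVA) / rho = 0.25, 0.27 or 0.28 SD.

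**Missing baselines.** A complete-case ANCOVA drops anyone without a baseline. At rho 0.3, losing three waitlist baselines (25 against 22) gives 0.569, so the gain is gone. Losing five (25 against 20) gives 0.585, worse than unadjusted. At rho 0.5 or 0.7 a gain remains.

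**Choice of SD for d.** Dividing by the ANCOVA residual SD would inflate d by 1/sqrt(1 - rho²) = 1.05, 1.15 or 1.40. Dividing a 0.5 SD difference by the change-score SD, sqrt(2(1 - rho)), would give 0.42, 0.50 or 0.65. The denominator therefore has to be named.

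**The case against.** The strongest reply is that nothing here is wrong. Randomisation makes the unadjusted difference unbiased, a general linear model can take a covariate, and this is a pilot that disclaims power. The precision gain rests on a correlation the documents do not give; at 0.3 it is slight. All of that stands, and it limits the point to an improvement.

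Three stronger readings are tempting, and the documents do not support them:

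- A reader might infer that ANOVA is the wrong estimator. It is a valid one; what is missing is a stated adjustment.
- A reader might infer that the outcome is undefined. The SAP's timing phrase points to the week-8 value, and the SAP says change from baseline explicitly where it means that. The later mention of observing changes leaves a doubt worth one clarifying sentence, no more.
- A reader might infer that uncertainty is concealed. The SAP plans means and SDs by group, so with the arm sizes a reader can work out the unadjusted interval. Printing it is good practice, not the repair of a concealment.

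It is also fair to say that adjustment has costs: a covariate reported after allocation is known, possible loss of participants without a baseline, and normal-theory intervals where the choice of Kruskal-Wallis suggests that skewed drinking data may be expected. These are reasons to specify the adjustment carefully and to keep the unadjusted estimate in view, not reasons to omit it.

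**Conclusion.** The point holds as a cheap improvement. The week-8 effect size is valid as planned but probably less precise than it could be, and it is to be reported without an interval. Under the stated assumptions the gain from adjustment runs from 3.5% to 28% of the CI width for rho between 0.3 and 0.7, and is nil below about 0.15. The case for printing a CI does not depend on rho. The case for adjustment also assumes that knowing the arm does not much alter the baseline report.

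The adjustment applies to alcohol use. The questionnaire list in section 5 shows no adherence measure, and Step 1, item 10 excludes screening data from use in the study, so no baseline adherence value is evident. A CI for the adherence effect size needs no baseline.

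**What to change.** Change the second paragraph of the Statistical Analysis Plan as follows:

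1. Name the week-8 alcohol measure and confirm that the outcome is its week-8 value.
2. Pre-specify as the lead estimate an ANCOVA of week-8 alcohol use on arm and the baseline value of the same measure. Report the unadjusted difference beside it, and keep Kruskal-Wallis as planned.
3. Give each difference and each standardised difference a 95% CI, by bootstrap or a robust method if drinking is skewed. Standardise by the unadjusted pooled SD.
4. Keep participants with a missing baseline in the model, for example by filling in the baseline mean pooled over arms.
5. State that adjustment assumes the baseline report is unaffected by knowledge of the arm. Report the baseline difference and the baseline completion dates by arm, and discuss any material gap between adjusted and unadjusted results.
6. For adherence, report a CI with the week-8 d whenever adherence is measured in both arms at week 8. Adjust it only if a baseline measure exists.

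The cost is SAP wording and one degree of freedom, with no new data collection. The validity cost is a lead estimate that relies on a self-reported covariate collected after allocation is disclosed; items 2 and 5 keep that visible.
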